10.0 EVALUATION DURING TREATMENT/INTERVENTION

Pre-treatment evaluations may be performed within 8 weeks of consent. After SRS, patients will be closely monitored for any evidence of toxicity, systemic illness or tumor progression. Acute toxicity assessment (see Appendix E) will occur by phone or clinic visit within 4 weeks (± 10 days) after the completion of radiotherapy. Follow-up clinic visits will take place 3 months, 6 months, 9 months, 12 months, 18 months and 24 months (± 8 weeks) after the completion of radiotherapy. At each follow-up visit, the investigators will complete the Spine Clinic Assessment form (see Appendix F). Spine MRI or CT will also be performed at the time of each follow-up, in accordance with routine standard of care.

Table 1: Pre-therapy and Follow-up Evaluations

Item	Pre-therapy (w within 8 weeks of consent)	Follow-up (3, 6, 9, 12, 18, 24 months \pm 8 weeks after the completion of SRS)
Inclusion/exclusion criteria	X	
CT myelogram or MRI perfusion	X	
Pathology diagnosis confirming metastatic disease	X	
Medical history	X	
Pregnancy test ¹	X	
Physical exam	X	X
Concomitant medications review	X	X
ECOG	X	X
Quality of Life assessments (MDASI and BPI) ²	X	X
Spine Clinic Assessment Form	X	X
MRI/CT scan ³	X	X
Adverse-event/toxicity assessment ⁴	X	X
Consent	X	

¹ For women of child-bearing potential, a urine or blood pregnancy test must be completed within 2 weeks prior to SRS.

- ² Patients will be asked to complete quality of life (MDASI and BPI) assessments at all timepoints, however this will remain optional. In instances where these questionnaires are not available in the participant's primary language, the participant will not be required to complete the questionnaire(s).
- ³ All patients are required to have MRI/CT based imaging at baseline and 3, 6, 9, 12, 18, and 24 months (\pm 8 weeks) after SRS. The imaging modality should remain constant for each patient throughout.
- ⁴ Only treatment-related adverse events will be reported. Acute toxicity assessment (see Appendix E) will occur by phone or clinic visit within 4 weeks (\pm 10 days) after the completion of radiotherapy.

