The organ at risk tolerances will be different for the two treatment arms and are presented in Appendix G (Single-Fraction) and Appendix H (Hypofractionated). The single-fraction treatment will be administered in one day while the hypofractionated treatment will be administered every other day. Total treatment time per fraction including set up will be 60-75 minutes per fraction.

Nausea, dysphagia and diarrhea will be treated according to standard institutional practice.

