11.2 Adverse Events (AE)

Defined

An adverse event is defined as the appearance of (or worsening of any pre-existing) undesirable sign(s), symptom(s), or medical condition(s) that occur after treatment. For this study, we consider reportable adverse events to include radiation Grade 3 (and above) toxicity as enumerated in Section 11.1. Adverse events should be reported to both the site PI and the MSK PI, please see Section 16.0.3.

Reporting Requirements

For non-serious adverse events, we will only be capturing toxicities that are possibly related to study participation. Adverse event monitoring will be continued for 24 months following the completion of SRS treatment or until the time of death if death occurs prior to the 24 month follow-up. Adverse events should be described using a diagnosis whenever possible, rather than individual underlying signs and symptoms. When a clear diagnosis cannot be identified, each sign or symptom should be reported as a separate Adverse Event. Adverse events will be reported within 14 days.

Adverse events will be assessed by the investigators according to the National Cancer Institute Common Terminology Criteria for Adverse Events (CTCAE) version 4.0 (<http://ctep.info.nih.gov>). If CTCAE grading does not exist for an adverse event, the severity of mild, moderate, severe, and life-threatening, corresponding to Grades 1-4, will be used.

As far as possible, each adverse event should be evaluated to determine:

1. The severity grade (CTCAE Grade 1-4)
2. Its duration (start and end dates or Ongoing at End of Study)
3. Its relationship to the study treatment (reasonable possibility that AE is related to study: No, Yes)
4. Action taken with respect to study (none, dose adjusted, temporarily interrupted, permanently discontinued, unknown, not applicable)
5. Whether medication or therapy was given (no concomitant medication/non-drug therapy, concomitant medication/non-drug therapy)
6. Whether it is serious, where a SAE is defined as in Section 17.2 (SAE)

All adverse events should be treated appropriately. If a concomitant medication or non-drug therapy is given, this action should be recorded on the Adverse Event form in CRDB. Once an adverse event is detected, it should be followed until its resolution or until it is judged to be permanent.

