patient has multiple eligible lesions, all of them will be treated within the randomized arm and each eligible lesion (non-contiguous lesions treated with a separate radiation contour) will be treated as a separate study unit. After the enrollment of the final patient, a 2-year follow up is planned. Three interim analyses are planned and will be conducted at the time of the DSMB annual review of the study. The O'Brien-Flemming boundary will be applied for assessing statistical significance. Specifically, the rejection regions in terms of the corresponding Z-scores are $Z > 3.09$, $Z > 2.06$, $Z > 1.63$ and $Z > 1.39$ for the three interim looks and the final look, respectively. We expect that very few patients will have multiple lesions and thus we do not plan to examine the correlation among multiple lesions from the same patients. Instead, the analysis of the primary endpoint will be conducted at lesion level as mentioned above. Data will be collected from all four centers and analyzed at MSKCC.

In consideration of the fact that a large cohort will be recruited, this study will be continuously monitored to protect patients from excess toxicity. For each arm, we anticipate that the true rate of any grade 4 toxicity within 24 months post SRS is less than 10%. All grade 4 toxicities or greater observed will be reviewed by the study chair. Moreover, using a stopping rule based on sequential probability ratio test (SPRT), each arm of the study is monitored for any grade 4 or above toxicities that are judged to be associated with the radiation treatment. This stopping rule specifies that for each arm, the study will be halted if any of the following conditions occur: >4 /first 15; >6 /first 35; >9 /first 55; or if more than 12 unacceptable toxicities are observed within 24 months post SRS when the last (75th) patient has completed the trial. When the true toxicity rate is 10%, this stopping rule has a probability of 0.1 to stop the trial. When the true toxicity rate is 20%, this stopping rule has a probability of 0.8 to stop the trial. For this stopping rule we will use each patient as a study unit.

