Toxicity outcomes and patterns of complications are summarized and tabulated in Section 11.0. Comparisons will be made using Wilcoxon rank sum tests and proportion tests. QOL results measured by MDASI scores and pain control results measured by BPI scores will also be summarized and compared between the two arms by Wilcoxon rank sum tests. As multiple measurements will be taken and thus multiple tests will be conducted, test p-values will be adjusted by the false discovery rate method.

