15.2 Randomization

Randomization will be centralized at MSKCC. Patients will be randomized to the single dose arm (24 Gy) or the multi-dose arm (27 Gy in 3 fractions). Ineligible lesions and other lesions not being treated on protocol will be treated according to standard of care at the physician's discretion. Immediately after consent is obtained at MSKCC and at participating sites, the RSA will register participants in the Protocol Participant Registration (PPR) system. Once the participant's eligibility is established, the registration will be finalized and the participants will

be randomized using the Clinical Research Database (CRDB). Randomization will be accomplished by the method of random permuted block, and will be stratified by institution, prior radiation history, and radioresponsiveness of the primary disease site (radioresponsive tumors include prostate, lung, breast, etc and non-responsive tumors include melanoma, renal cell, colon and sarcoma). After the treatment arm is determined by randomization, the RSA will notify the research staff and/or investigators at MSKCC and participating sites of the treatment arm and participant ID via email within 24 hours of randomization.

Data will be collected at other centers and sent to the RSA(s) at MSKCC according to Table 6. Compiled data will be submitted to the biostatisticians at MSKCC for analysis.

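### The toxicity comparison counts non-serious events only if an investigator who can know the arm judges them related, so arm-dependent attribution could bias it, mainly for non-fracture Grade 3 events

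*Combined protocol and SAP*

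**What the plan says.** Two passages set the entry condition for adverse events, and they differ. Footnote 4 to Table 1 in Section 10.0 states: "Only treatment-related adverse events will be reported". Section 11.2 is narrower in scope and looser in threshold: "For non-serious adverse events, we will only be capturing toxicities that are possibly related to study participation". The toxicity footnote to Table 6 refers back to Section 11 for what must be submitted.

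Section 11.2 makes Grade 3 and above radiation toxicity reportable and names the assessors: "Adverse events will be assessed by the investigators according to the National Cancer Institute Common Terminology Criteria for Adverse Events (CTCAE) version 4.0". Relatedness is a No/Yes item on a reasonable-possibility standard.

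On knowledge of the arm, Section 15.2 says "the RSA will notify the research staff and/or investigators at MSKCC and participating sites of the treatment arm and participant ID via email". Section 9.0 shows that the schedules are easy to tell apart: "The single-fraction treatment will be administered in one day while the hypofractionated treatment will be administered every other day". No masking of assessors is described. The central review in Section 12.0 is of imaging and does not cover the cause of adverse events.

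Section 2.0 makes the comparison of radiation-related toxicity a secondary objective. For toxicity and complications, Section 14.0 says: "Comparisons will be made using Wilcoxon rank sum tests and proportion tests". The stopping rule in the same section counts "any grade 4 or above toxicities that are judged to be associated with the radiation treatment".

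**The concern.** Randomisation protects a comparison of all events of a given type. It does not protect a comparison of events that have first passed a judgement made with the arm known. All these patients had spinal surgery within the previous 8 weeks (Section 6.1) and have metastatic cancer. Many events therefore have more than one plausible cause. The surgical complications in Table 2 include wound problems, pneumonia, radiculopathy and gastrointestinal bleeding, which overlap the skin, lung, neurological and GI toxicities monitored under Section 11.1. The same event could be called radiation-related in one arm and surgical or tumour-related in the other.

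Section 14.0 says that, if local control is comparable, physicians will choose between schedules on factors such as cost and toxicity risk. A biased toxicity comparison could therefore affect practice even though it is secondary. A non-serious event judged unrelated need not be recorded as an adverse event, so an all-cause comparison could not be reliably rebuilt at analysis.

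**Working it through.** **The plan's own toxicity figure.** The plan gives no power or error rate for the arm comparison. Its only operating characteristics for toxicity are those of the stopping rule: stop if counts exceed 4 of 15, 6 of 35, 9 of 55 or 12 of 75. An exact binomial recursion over the four looks gives a stopping probability of 0.088 at a true rate of 10% (stated 0.1) and 0.822 at 20% (stated 0.8). These agree at the precision given, and the rule's arithmetic is not in dispute.

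**Inputs for the comparison.**
- From the plan: 75 patients per arm (Section 14.0); 6.8%, the crude rate of Grade 3 or higher oesophageal toxicity after single-fraction SRS (Section 3.7); below 1% for more significant toxicity (Section 11.1); 10%, the ceiling that Section 14.0 expects for Grade 4 toxicity.
- Assumed: applying those rates to both arms, the added rates of 5% and 15%, the attribution shares, and a two-sided 5% test without the planned false-discovery-rate adjustment. Section 14.0 gives no significance level for toxicity.

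**Formula.** Recorded rate = true rate × share attributed. Test statistic z = (a − b) / √(2·p̄(1 − p̄)/75), where a and b are the observed proportions and p̄ is their mean; reject if |z| > 1.96. Rejection probabilities come from exact enumeration of two binomials. The true rate is the same in both arms, so every rejection is a false positive.

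| True rate, both arms | Recorded, 90% vs 60% attributed | False positives | Recorded, 90% vs 75% attributed | False positives |
|---|---|---|---|---|
| 1% | 0.9% vs 0.6% | 0.4% | 0.9% vs 0.75% | 0.4% |
| 5% | 4.5% vs 3.0% | 7.0% | 4.5% vs 3.75% | 5.3% |
| 6.8% | 6.12% vs 4.08% | 8.4% | 6.12% vs 5.10% | 5.8% |
| 10% | 9.0% vs 6.0% | 11.0% | 9.0% vs 7.5% | 6.5% |
| 15% | 13.5% vs 9.0% | 14.0% | 13.5% vs 11.25% | 7.0% |

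With equal attribution the rate is about 5% in the last four rows. At 1% there are too few events to reject often under any attribution.

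**A hidden difference.** Take assumed true rates of 20% and 10%. If every event counts, power is 41%. With 80% attributed in both arms (16% vs 8%) it is 33%. With 60% attributed in the higher-rate arm and 90% in the other, the recorded rates are 12% and 9%, and the chance of finding the difference in the right direction is about 9%.

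**Monitoring.** If only 75% of truly radiation-caused Grade 4 or higher events were attributed, a true 20% would be counted as 0.20 × 0.75 = 15%, and the stopping probability would fall from 0.82 to 0.44. The 75% is an assumption.

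**The case against.** The strongest reply is that the filter leaks less than it seems.

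- **Fracture.** Section 14.0 classes vertebral body fracture as a treatment-related toxicity by type, Section 11.1 monitors it in everyone, and imaging is scheduled at baseline and six follow-ups. Fractures could be re-read by arm from stored scans. This stands. A reader might infer that the fracture comparison, the toxicity the plan names as distinguishing the schedules, is the one most at risk and cannot be recovered. The documents do not support that.
- **Other all-cause data.** Hospitalisation within 30 days is an SAE whatever its cause (Section 17.2), and Table 6 asks for a form at every hospitalisation. ECOG, MRC strength and ASIA are assessed irrespective of cause. Surgical complications are also monitored (Sections 4.1 and 11.1). This narrows the gap, but no all-cause adverse event comparison is planned.
- **Threshold.** A possibly-related standard, applied to prespecified organ classes, is inclusive, and nothing in the documents points to a share as low as 60% in one arm. This stands; the shares are illustrative.
- **Prompting.** The plan does tell investigators to expect more fractures after single-fraction treatment. The severe oesophageal events in Section 3.7, however, all occurred with oesophageal manipulation or radiation-recall chemotherapy, so that passage offers alternative causes as much as an arm to suspect.
- **Estimand.** The stated objective is radiation-related toxicity. An all-cause comparison answers a different question and carries background noise. This is a good reason to add it without replacing the planned comparison.

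The contents of the toxicity and clinic forms (Appendices E and F) are not shown, so they may record more than the text requires.

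**Conclusion.** The point holds in a limited form. For non-serious adverse events the plan makes judged relatedness a condition of entry, leaves that judgement to investigators who can know the arm, and compares arms on the result. That permits an avoidable bias in a secondary comparison, mainly for non-serious Grade 3 events other than fracture. Lack of masking is inferred from the arm notification and the absence of any masking text; the documents do not use the term open-label.

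At true rates of 5% to 10%, a range that contains the documented 6.8%, false positives rise from about 5% to between 7% and 11% under a wide attribution gap (90% versus 60%), and to between 5% and 7% under a narrower one (90% versus 75%). The false-discovery-rate adjustment deals with multiplicity and does not remove the bias. A reader might infer that attribution will differ by arm, or that the toxicity results will be invalid. The documents show only that attribution could differ; they give no evidence on whether or how far it will. This is a cheap improvement, not a defect that undermines the trial.

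**What to change.** 1. Reconcile Table 1 footnote 4 (treatment-related, all events) with Section 11.2 (possibly related, non-serious events).
2. In Section 11.2, Table 1 footnote 4 and the Table 6 toxicity footnote, record every Grade 3 or higher event in the organ classes already listed in Section 11.1, whatever its judged cause. Keep the existing No/Yes relatedness item as a recorded field and stop using it as an entry filter.
3. In Section 14.0, keep the radiation-related comparison and add a prespecified all-cause Grade 3 or higher comparison by arm, reported beside it.
4. Show the DSMB all-cause Grade 4 or higher counts by arm next to the attributed counts. Leave the stopping rule unchanged.

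The cost is protocol and form wording and somewhat more adverse event forms, limited to organ classes already monitored. Background disease and surgical events will add noise to the all-cause comparison, which is why it should accompany the radiation-related analysis and not replace it.

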11.0 TOXICITIES/SIDE EFFECTS

11.1 Toxicities/Complications

Subjects will be monitored for surgical complications. Our retrospective study found that major surgical complications occurred in 14.3% patients within 30 days of surgery. Among those patients that suffered complications from surgery within 30 days, Table 2 below depicts the likelihood of complications^{6,39}:

Table 2: Postoperative Complications

wound infection/dehiscence	2.9%
hardware fracture	2.8%
pneumonia	2.1%
pulmonary embolism	2.1%
postop hematoma	0.7%
radiculopathy	0.7%
stroke	0.7%
gastrointestinal bleed	0.7%

Cerebrospinal fluid leak is a rare complication, occurring after less than 5% of operations. Neurologic injury is an exceedingly rare post-operative complication, occurring after far less than 1% of operations.

Patients will also be monitored for radiation toxicity including: acute (\leq 90 days from the start of treatment) and late ($>$ 90 days) toxicity. All patients are going to be monitored for skin, subcutaneous tissue, spinal cord and fracture toxicity. In addition, patients undergoing cervical radiation will be monitored for mucous membrane, pharynx and esophagus, larynx and upper GI toxicity. Patients undergoing thoracic radiation will be monitored for upper and lower GI, lung and heart toxicity. Patients undergoing lumbar radiation will be monitored for genitourinary and lower GI toxicity. The severity of the toxicity will be graded according to Appendix I (Acute Radiation Toxicity) and Appendix J (Late Radiation Toxicity) based on the Radiation Therapy Oncology Group classification schema.

Low-grade radiation-related toxicity may include fatigue, skin erythema, subcutaneous fibrosis and bone pain. More significant toxicity is rare ($<$ 1%) and may include esophagitis,

pericarditis, diarrhea, nausea, vomiting, myelosuppression, myelitis, acute radiation pneumonitis, late pulmonary fibrosis, esophageal stricture, small bowel obstruction and radiation enteritis.

Participants should not be or become pregnant during the course of treatment because the radiation used in this study may be teratogenic. Participating sites should notify the MSK PI if an external participant becomes pregnant.

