3.7 SRS Toxicity Profile

Multiple studies reported low risk of toxicity after spinal SRS. The majority of events involved Grade 1 or 2 skin and esophageal toxicity²¹. To date, hypofractionated treatment of the spine has not been reported to result in Grade 3 or 4 neurologic toxicity. Single cases of Grade 3 vomiting, diarrhea, costochondritis and dysphagia were reported after hypofractionated treatment^{29,30}. To date, radiation literature describes nine cases of radiation myelopathy that have been attributed to single-fraction spinal radiation, confirming that this is an exceedingly rare consequence of spinal radiation³¹. Furthermore, in this institution no cases of radiation-induced myelopathy have been observed using cord point-maximum dose of 14Gy in patients without prior radiation history. A crude rate of Grade ≥ 3 esophageal toxicity of 6.8% was reported in our institution following single-fraction spine SRS³². Two Grade 4 acute esophageal toxicities, four Grade 4, and one Grade 5 late esophageal toxicities occurred. All of these events occurred in patients with either iatrogenic esophageal manipulation or with a history of radiation recall chemotherapy.

Some evidence suggests that administration of individual radiotherapy doses of 20 Gy or greater per fraction may lead to an increased risk of vertebral compression fracture³³. These findings remain limited as there are few studies that have compared single-fraction and hypofractionated SRS dosing schemes particularly in the post-operative period, thereby underscoring the clinical value of this prospective trial.

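### Section 11.1 names the esophagus as a monitored organ only for cervical patients, so its thoracic list does not clearly cover a toxicity that Section 3.7 reports at 6.8% (Grade 3 or above) after single-fraction SRS

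*Combined protocol and SAP*

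**What the plan says.** Section 11.1 gives one list for everyone and then adds organs by treated region.

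- All patients: "All patients are going to be monitored for skin, subcutaneous tissue, spinal cord and fracture toxicity".
- Cervical: "patients undergoing cervical radiation will be monitored for mucous membrane, pharynx and esophagus, larynx and upper GI toxicity".
- Thoracic: "Patients undergoing thoracic radiation will be monitored for upper and lower GI, lung and heart toxicity".
- Lumbar: genitourinary and lower GI.

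The same section closes with a general paragraph that is not tied to region. It reads in part "More significant toxicity is rare ($<$ 1%) and may include esophagitis", and esophageal stricture comes later in the same list.

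Section 3.7 gives the institutional experience: "A crude rate of Grade ≥ 3 esophageal toxicity of 6.8% was reported in our institution following single-fraction spine SRS". It continues: "Two Grade 4 acute esophageal toxicities, four Grade 4, and one Grade 5 late esophageal toxicities occurred". It then qualifies this: "All of these events occurred in patients with either iatrogenic esophageal manipulation or with a history of radiation recall chemotherapy". It gives no denominator, no count of Grade 3 events and no spinal level. Section 3.7 also says that most toxicity reported after spinal SRS was Grade 1 or 2 and affected skin or esophagus.

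**The concern.** The esophagus runs through the chest, and esophageal toxicity is the only severe single-fraction toxicity for which Section 3.7 states a rate. For hypofractionated treatment that section cites only single Grade 3 cases, dysphagia among them. A site that follows the region lists literally has no instruction to ask a thoracic patient about the esophagus.

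Two uses of the data depend on even ascertainment. Comparing radiation toxicity between the arms is a secondary objective (Section 2.0). Section 14.0 says that if local control proves comparable, physicians will choose on factors such as cost and toxicity. If esophageal events are recorded less completely in thoracic patients, the observed difference between arms could be too small, and the four centers could differ in what they record.

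**Working it through.** **1. The lists side by side (Section 11.1)**

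| Group | Organs named | Esophagus named? |
|---|---|---|
| All patients | skin, subcutaneous tissue, cord, fracture | no |
| Cervical | mucous membrane; pharynx with esophagus; larynx; upper GI | yes |
| Thoracic | upper GI; lower GI; lung; heart | no |
| Lumbar | genitourinary; lower GI | no |

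**2. Does upper GI include the esophagus?** In the cervical list the two are separate items. If the terms keep the same meaning from one sentence to the next, the thoracic list leaves the esophagus out. If the items were meant to overlap, it is covered. The supplied text does not define upper GI, and the contents of the grading tables (Appendices I and J) were not available. The wording therefore does not settle the matter.

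**3. What else would capture a thoracic esophageal event?**

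- Section 10.0 and Table 1: monitoring for toxicity of any kind, an acute assessment within 4 weeks (± 10 days) of SRS, and a toxicity assessment at 3, 6, 9, 12, 18 and 24 months, with no limit by spinal level.
- Section 12.0: treatment-related toxicity is a secondary endpoint at each follow-up visit.
- Sections 11.1 and 11.2: esophagitis and stricture are enumerated without regional limit, so they are reportable at Grade 3 or above.
- Section 14.0: the per-arm stopping rule counts any radiation-associated toxicity of Grade 4 or above, in any organ.
- Section 17.2: Grade 4-5 toxicity directly due to treatment (vertebral fracture excepted) and specified hospitalizations are serious adverse events.

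These routes cover severe events well. Grade 1-2 events fall outside the Section 11.2 reporting threshold, so they depend most on what is asked at the visit.

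**4. Scale.** The 6.8% cannot be reproduced, because its numerator and denominator are not given. Taking it as stated, with n = 75 per arm (Section 14.0):

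- Expected Grade 3 or above events = n × p = 75 × 0.068 = 5.1. P(at least one) = 1 − 0.932^75 = 0.995.
- At 1%, the ceiling of Section 11.1's own figure: 75 × 0.01 = 0.75. P(at least one) = 1 − 0.99^75 = 0.53.

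The thoracic share is not stated. The next table assumes 30%, 50% or 70% of the arm, rounded to whole patients, with 6.8% applying at every level:

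| Assumed share | Patients | Expected events | P(at least one) |
|---|---|---|---|
| 30% | 22 | 22 × 0.068 = 1.5 | 0.79 |
| 50% | 38 | 38 × 0.068 = 2.6 | 0.93 |
| 70% | 52 | 52 × 0.068 = 3.5 | 0.97 |

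These are events expected to occur. The number missed lies between zero and these counts, and nothing in the documents places it within that range.

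Of the Grade 4-5 events in Section 3.7, 2 were acute and 4 + 1 = 5 were late, so 5 of 7 were late.

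**5. Effect on the comparison.** Let p1 and p2 be the true rates in the two arms, s the thoracic share and m the fraction of thoracic events missed, with s and m the same in both arms and each arm's rate the same at every level. The expected observed difference is then (1 − s·m)(p1 − p2). It shrinks toward zero in absolute terms if m > 0 and is unchanged if m = 0. The documents give no value for m.

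**The case against.** A reader might infer from the region lists that thoracic patients have no esophageal monitoring at all. The documents do not support that. Scheduled toxicity assessments apply to everyone, severe esophagitis and stricture are reportable whatever the level, and a center could reasonably read upper GI as including the esophagus. What sites actually ask is set by the Acute Toxicity and Spine Clinic Assessment forms (Appendices E and F). Their contents were not available, and they may already contain an esophageal item.

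A reader might also take the 5.1 expected events, or the thoracic part of them, as the size of the loss. That does not follow either. Section 3.7 says the events it describes all occurred in patients with esophageal manipulation or radiation recall chemotherapy. It is not clear whether this refers to the seven Grade 4-5 events or to everything behind the 6.8%. Applying one rate to every patient at every level is therefore only a rough guide. Section 6.2 does not exclude such histories as such; it bars named radiosensitizing drugs within one week of radiation.

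Nor is the stopping rule shown to be compromised: it counts any organ, and Grade 4-5 events also come in through serious adverse event reporting.

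All of this stands, and it narrows the point. It does not remove it. The general provisions let an event be recorded, but they do not tell a site to ask a thoracic patient about the esophagus, and the one place that names organs by region leaves it out.

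**Conclusion.** The point holds in limited form. Section 11.1 states a region-specific rule whose thoracic list does not clearly cover the esophagus, while Section 3.7 reports 6.8% Grade 3 or above esophageal toxicity after single-fraction SRS. The plausible consequence is uneven questioning between sites, with some under-recording of lower-grade or late esophageal events in the toxicity comparison. Loss of severe events is less likely, given the other routes. The size of any under-recording cannot be estimated; the 1.5 to 3.5 expected thoracic events rest on an assumed share and a uniform rate, and are not missed events.

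Separately, Section 11.1 describes significant toxicity including esophagitis as under 1%, against 6.8% in Section 3.7. The two passages need reconciling.

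Severity is minor to moderate and confidence moderate. The rating would fall to a wording correction if Appendices E and F already ask every patient about the esophagus, and rise if they follow the region lists.

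**What to change.** 1. In Section 11.1, add pharynx and esophagus to the thoracic list. Alternatively, have every patient assessed on every toxicity category at the acute assessment and each follow-up visit, with the treated level recorded. The second option also removes any doubt over what upper GI means.
2. Check that the Appendix E and F forms match the revised list.
3. Reconcile the figure of under 1% in Section 11.1 with the 6.8% in Section 3.7, stating the population to which each applies.

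The cost is a line or two of protocol text in an amendment, about one form item if it is missing, and roughly a minute of questioning per visit. No added visit or procedure is needed.
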